10. SECONDARY ENDPOINTS ANALYSES

Each secondary endpoint will be analyzed and summarized using appropriate statistical methods, and results will be presented by treatment group unless otherwise specified. Tables or figures will be used where appropriate.

1. Ventilator-Free Days (VFDs) defined as 28 days minus the total duration (in days) of invasive mechanical ventilation during the first 28 days post-randomization.
 - Participants who do not survive through Day 28 will be assigned 0 VFDs.
 - Participants who remain mechanically ventilated on Day 27 will be assigned 0 VFDs.
 - Participants transferred to long-term acute care hospitals (LTACHs) will be assigned 0 VFDs.
 - Participants who withdraw from the study will be considered as having missing data.Differences in VFDs between treatment arms will be analyzed using a two-sample parametric t-test. Descriptive statistics (mean, standard deviation, median, quartiles, and range) will also be presented in summary tables.
2. Total RSFDs without last-off approach defined as 28 minus the cumulative number of days on any form of respiratory support within 28 days of randomization, without the last-off rule applied. Participants who die before Day 28 will be assigned 0 RSFDs.

Differences in RSFDs between treatment arms will be analyzed using a two-sample parametric t-test. Descriptive statistics (mean, standard deviation, median, quartiles, and range) will also be presented in summary tables.

3. Mortality will be evaluated as a time-to-event outcome through 28 days and 180 (± 42 days). Analyses will mirror those described in Section 9, including Kaplan–Meier survival curves, log-rank tests, and Cox proportional hazards models (adjusted and stratified by baseline creatinine clearance). In addition, we will test for an interaction between treatment group and period (during- vs. post-treatment) to determine if treatment effects on mortality vary over time.
4. Duration of mechanical ventilation among participants who survive through Day 28, the total number of days on invasive mechanical ventilation will be calculated. Participants transferred to LTACHs will be assigned 28 days. Differences between treatment arms will be analyzed using a two-sample parametric t-test. Descriptive statistics (mean, standard deviation, median, quartiles, and range) will also be presented in summary tables.
5. Duration of respiratory support (with Last-Off Approach) among Day 28 survivors, the number of days on any qualifying respiratory support (applying the last-off approach) will be summarized. Participants transferred to LTACHs will be assigned 28 days. Differences between treatment arms will be analyzed using a two-sample parametric t-test. Descriptive statistics (mean, standard deviation, median, quartiles, and range) will also be presented in summary tables.
6. Oxygenation ($\text{PaO}_2/\text{FiO}_2$ ratio) measured daily on study days 1–7 will be visualized using boxplots stratified by treatment arm.
7. ICU-free days, defined as 28 minus the number of days in the intensive care unit (ICU) during the first 28 days post-randomization.
 - Participants who do not survive through day 28 will be assigned zero ICU-free days.
 - Participants who remain in the ICU on day 27 will be assigned zero ICU-free days.
 - Participants who are transferred to LTACH facilities will be assigned zero ICU-free days.
 - Participants who withdraw from the study will be considered as having missing data.Differences in ICU-free days between treatment arms will be analyzed using a two-sample parametric t-test. Descriptive statistics (mean, standard deviation, median, quartiles, and range) will also be presented in summary tables.
8. CMV DNA detection in plasma and endotracheal aspirate (ETA) by day 28 (>0 IU/mL, >1000 IU/mL), defined as positive CMV PCR from ETA, plasma, or serum specimens.
The analysis will be conducted by the unblinded protocol statistician.
Differences in CMV DNA detection in plasma and endotracheal aspirate between treatment arms will be evaluated under the competing risk framework of Fine and Gray (10). Cumulative incidence estimates will be evaluated, and Gray's test p-value will be used to test the difference between arms accounting for death as competing risk.
 - This analysis will include death as a competing risk if it occurs on the same day of the last negative CMV test date.
 - Any CMV reactivation will be considered, even those which were below the level of quantification but greater than 0.
9. A comprehensive list of all reportable AEs of Grade 3 or higher by day 28 will be provided, including onset date, AE verbatim, MedDRA code, SAE/EAE, study day, severity grade, relationship to study drug, outcome, and duration days.

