3. GENERAL DATA ANALYSIS CONSIDERATION

3.1 Analysis Set(s)

The **Intent-to-Treat (ITT) Analysis Set** will include all enrolled and randomized participants. However, one exception applies: participants who are withdrawn from the study before receiving any dose of the study drug will not undergo study procedures and will be excluded from the ITT analysis. Participants who are withdrawn after receiving at least one dose will continue to receive safety assessments (e.g., creatinine and complete blood count with differential) for up to 48 hours. Although no study bio-samples will be collected after withdrawal, clinical data available in the medical record (e.g., respiratory-support-free days) will continue to be collected per protocol, and such participants will be included in the ITT analysis. **The ITT set will serve as the primary analysis population.**

Two modified Intent-to-Treat (mITT) Analysis Sets will also be defined:

The first mITT set will exclude participants who are withdrawn from the study for any reason after receiving at least one dose of study drug. Reasons for withdrawal may include, but are not limited to: participant withdrawal of consent, inability or unwillingness to comply with study procedures, refusal to continue participation by the participant or their legally authorized representative (LAR), or an initial positive CMV LFA test followed by a confirmatory negative CMV ELISA result.

The second mITT set will include only those participants who survive and are followed through day 28.

In addition, a **classical ITT set**, which includes all randomized participants regardless of treatment receipt or study completion, will be retained for completeness.

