8. PRIMARY ENDPOINT ANALYSES

The primary endpoint, respiratory-support-free days (RSFDs), is defined as 28 days minus the number of days a participant received respiratory support (including invasive mechanical ventilation, non-invasive ventilation with CPAP or bi-level CPAP and PEEP ≥ 5 cmH₂O, or high-flow nasal cannula oxygen with a flow rate ≥ 30 L/min) through Day 28 following randomization.

- Participants who do not survive through Day 28 will be assigned zero RSFDs.
- Participants who remain on respiratory support on Day 27 will be assigned zero RSFDs.
- Participants transferred to long-term acute care hospitals (LTACHs) will be assigned zero RSFDs.
- Participants who withdrew consent, refused further participation by themselves or a legally authorized representative (LAR), and for whom no further data were collected, or who withdrew due to study closure within the first 28 days will be considered missing for the RSFD endpoint.

RSFDs will be summarized descriptively using the mean, standard deviation, median, and range by treatment group. To formally test the primary hypothesis that the mean difference in RSFDs between treatment arms differs from zero, a two-sample parametric t-test will be used. This test is appropriate even if the normality assumption is mildly violated, given its robustness for moderate sample sizes ($n > 25$). As a confirmatory approach, a two-sample permutation t-test will also be performed. This nonparametric test does not require distributional assumptions and is valid under the weaker condition of exchangeability, which is satisfied in the randomized trial setting.

To further improve statistical efficiency and precision, the semiparametric efficient and robust method of Davidian et al. [7, 8] will be employed to estimate the mean difference between arms, along with its 95% confidence interval. This method adjusts for baseline characteristics predictive of the primary outcome and is more powerful than a conventional ANCOVA or t-test when baseline adjustment is warranted. If data on

the primary endpoint are missing for reasons other than death, the analysis will appropriately account for the missing data mechanism, as described in Protocol Section 6.4.1.

In addition to the ITT analysis, the primary endpoint will also be analyzed in a classical intent-to-treat (cITT) and two modified intent-to-treat (mITT) populations.

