5.2.1 Secondary Endpoints

1. VFDs (defined to be 28 days minus the duration of mechanical ventilation through day 28 since randomization [a key secondary endpoint]). Participants who do not survive through day 28 are assigned zero VFDs.
2. Total RSFDs (calculated as 28 days minus each day of respiratory support through day 28 since randomization). Participants who do not survive through day 28 are assigned zero respiratory-support-free ventilator-free days.
3. Mortality by day 180 (day 28, day 180, time-to-event).
4. Duration of mechanical ventilation (among survivors) by day 28.
5. Duration of respiratory support (among survivors) by day 28.
6. Oxygenation (PaO₂/FiO₂ ratio) daily on study days 1-7.
7. ICU-free days by day 28.
8. CMV DNA detection in plasma and endotracheal aspirate (ETA) by day 28 (>0 IU/mL, >1000 IU/mL).
9. Number of patients with reportable adverse events of Grade 3 or higher by day 28.

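### SAP section 10 scores VFDs and ICU-free days as missing on withdrawal even where the data were collected, unlike the RSFD rule in SAP section 8

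*SAP*

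**What the plan says.** **Secondary endpoints.** SAP section 10, item 1 (VFDs) lists its scoring rules as bullets. One is "Participants who do not survive through Day 28 will be assigned 0 VFDs"; another is "Participants who withdraw from the study will be considered as having missing data". Item 7 (ICU-free days) has the same pair of rules. Neither item limits the withdrawal rule by reason, timing or availability of data. Item 2 (total RSFDs) has only the death rule, "Participants who die before Day 28 will be assigned 0 RSFDs", and says nothing about withdrawal.

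**Primary endpoint.** SAP section 8 is narrower. After consent withdrawal or refusal, RSFDs are missing only for those "for whom no further data were collected". A second limb covers participants "or who withdrew due to study closure within the first 28 days will be considered missing for the RSFD endpoint"; that limb has no data condition.

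**Analysis set and follow-up.** SAP section 3.1 says that, for participants withdrawn after at least one dose, clinical data in the medical record "will continue to be collected per protocol, and such participants will be included in the ITT analysis". Its list of reasons for withdrawal includes "an initial positive CMV LFA test followed by a confirmatory negative CMV ELISA result". Protocol sections 6.2.4 and 7.5 say the same about follow-up and inclusion, and section 7.5 limits collection to what the signed consent allows. Section 7.5 also makes an exception: participants whose first dose was late, where this is found before five doses, have no further data collected and are outside the primary population.

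**Link between endpoints.** SAP section 5 applies the RSFD approach to the quantitative secondary endpoints, naming VFDs. Protocol section 5.2.1 states the zero rule without a withdrawal exception: "Participants who do not survive through day 28 are assigned zero VFDs".

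**The concern.** Read literally, section 10 discards ventilation and ICU data that the plan elsewhere says it will keep collecting, for participants it keeps in the primary set. RSFDs and VFDs would then be analysed on different participants under the same ITT label. For VFDs and ICU-free days, the ITT analysis would also drop the participants whose exclusion defines the first mITT set, so the two sets would no longer be distinct.

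The scoring of deaths is also left open. A participant who withdraws and is known to have died by Day 28 satisfies two bullets in the same list, one giving 0 and the other giving missing, and no order is stated. The programmer would have to choose.

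Losing ELISA-negative participants should cost only precision, since that result is not expected to depend on arm. Protocol section 7.5 also lists withdrawal for severe side effects and by investigator decision for safety. Those could differ by arm, and deleting such participants when their outcomes are known could bias the comparison.

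**Working it through.** **1. The rules applied to the same participant**

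| Participant | RSFD (SAP 8) | VFD and ICU-free days (SAP 10) |
|---|---|---|
| Dosed, withdrawn for negative ELISA, chart complete | Scored | Missing |
| Dosed, consent withdrawn, record data still collected as consent allows | Scored | Missing |
| Dosed, consent withdrawn, nothing further collected | Missing | Missing |
| Dosed, withdrawn by the investigator, record shows death by Day 28 | 0 | 0 and missing both apply |
| Late first dose found before five doses (protocol 7.5) | Outside the primary set | Outside the primary set |

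The problem lies in rows 1, 2 and 4. Rows 3 and 5 show no conflict.

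**2. The plan's own sample size.** Inputs from SAP section 2.5 and protocol section 6.1.1: difference 2.74 days, SD 9.4, two-sided 5%, power 85%. The two-sample t-test calculation gives 212.3, so 213 per arm and 426 in total, as stated. Power at 213 per arm is 85.1%, in agreement with protocol Table 6-2.

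**3. Precision.** The planned ELISA-negative discontinuation is 2%, and 0.02 × 500 = 10 participants, or 5 per arm. With the same difference and SD:

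- 250 per arm: power 90.19%
- 245 per arm: power 89.61%
- loss: 90.19 − 89.61 = 0.58 points

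The increase from 426 to 500 already allows for this discontinuation. The 2.74 days and SD 9.4 come from phase 2 VFD data, so they suit VFDs; no corresponding figures are given for ICU-free days.

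**4. Possible bias (illustration; the withdrawal figures are assumed).** Suppose one arm loses an extra fraction x of its participants, whose true mean VFD is w, and the arm's full mean is 17.75 (the overall mean in protocol Table 6-1). The retained mean is (17.75 − xw)/(1 − x), so the arm mean shifts by x(17.75 − w)/(1 − x).

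| Shift in days | x = 1% (2.5 of 250) | x = 2% (5 of 250) | x = 3% (7.5 of 250) |
|---|---|---|---|
| w = 12 | 0.06 | 0.12 | 0.18 |
| w = 6 | 0.12 | 0.24 | 0.36 |
| w = 0 | 0.18 | 0.36 | 0.55 |

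Example: 0.03 × 17.75 / 0.97 = 0.55. The range is 2% to 20% of 2.74 days. The standard error of the difference is 9.4 × √(2/250) = 0.84, so the shifts are 0.07 to 0.65 standard errors (using the reduced number in the affected arm). With no true difference, the two-sided 5% test would reject in about 5.1% to 9.9% of trials. Equal fractions with equal means in both arms give no shift.

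**The case against.** **The line may be shorthand for section 8.** SAP section 5 carries the RSFD approach over to VFDs, so a careful programmer might supply the missing condition. But section 8 shows that the condition was written out where it was meant, and SAP section 12 announces no separate rule for secondary endpoints. The programmer should not have to infer it.

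**Section 10 speaks of participants who withdraw, while section 3.1 speaks of those who are withdrawn.** On that reading the ELISA-negative group would escape the rule. But section 3.1 lists the negative ELISA alongside withdrawal of consent as one kind of event, so the distinction is not maintained.

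**Membership of the ITT set with a missing endpoint is not a logical contradiction.** This stands. The objection to the rule is that it throws away collected outcomes, not that the set definition is broken.

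**The size is small and the bias is hypothetical.** This also stands. Protocol section 4.5.2 says the study is not specifically powered for secondary endpoints. SAP section 4 reports that enrolment was closed following the October 2024 DSMB meeting, and no final numbers are given, so 250 per arm is a planning figure. The top of the bias range needs a 3-point excess in one arm with every deleted participant truly scoring 0. Protocol section 9.13 keeps participants in follow-up when study drug is stopped for recurrent neutropenia, which makes withdrawal for that toxicity less likely.

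**Not every dosed withdrawal has data.** Correct: the late-first-dose group in protocol section 7.5 does not, and consent may limit collection for others. A rule that every post-dose withdrawal must be scored would therefore also be wrong.

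**Conclusion.** The concern holds as an inconsistency in a scoring rule that affects the key secondary endpoint, with a small expected effect. The unconditional line conflicts with the continued collection described in SAP section 3.1 and protocol sections 6.2.4 and 7.5, and departs from the rule for RSFDs after consent withdrawal or refusal. It also leaves the score of a withdrawn participant with a known death undetermined. The measurable cost is about 0.6 points of power, assuming 250 per arm and the planned 2% discontinuation. The bias range of 0.06 to 0.55 days rests wholly on assumed withdrawal excesses and outcomes.

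A reader might infer three stronger things that the documents do not support:

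- That the VFD comparison is biased. This needs withdrawals with collected data to differ by arm in number or in outcome, and no counts by arm are given.
- That consent withdrawals with no further data add to the problem. Section 8 makes them missing for RSFDs as well.
- That the RSFD analysis shares this fault. For consent withdrawal and refusal, section 8 has the data condition; only its study-closure limb lacks one.

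**What to change.** In SAP section 10, items 1 and 7, replace the withdrawal line with: *Participants in the analysis set who withdraw are scored from the record data collected as the consent allows, and are missing only where the data needed to determine the endpoint through Day 28 were not collected; a death by Day 28 in those collected data scores 0.* Apply the same sentence to item 2, which has no withdrawal rule.

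Restricting the sentence to the analysis set leaves the late-first-dose exception in protocol section 7.5 as it is. Section 8 should not be copied in whole: its study-closure limb has no data condition and would again discard collected values. The primary-endpoint rule in section 8 can otherwise stay unchanged.

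The cost is a wording change in three items of section 10 and the matching derivation code. It needs no data beyond what protocol section 7.5 already continues to collect.

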5. GENERAL ANALYSIS METHODS

Primary Endpoint

To evaluate the primary hypothesis—that the mean difference in respiratory support-free days (RSFDs) between the two treatment groups is significantly different from zero—we will use a two-sample parametric t-test as the primary statistical test. This test is known for its robustness to violations of normality when the sample size is sufficiently large ($n > 25$), as is the case in this trial.

To support and validate the primary analysis, we will also conduct a two-sample permutation t-test. This nonparametric test requires only the assumption of exchangeability, which is satisfied in the context of a randomized controlled trial. The permutation test provides a distribution-free confirmatory approach, reinforcing the robustness of our findings.

In addition, we will apply the semiparametric efficient and robust estimation procedure proposed by Davidian et al. [7,8] to estimate the mean treatment difference in RSFDs along with a 95% confidence interval. This method adjusts for baseline covariates predictive of the outcome, thereby improving both statistical efficiency and precision relative to unadjusted comparisons or traditional ANCOVA. This analysis also accommodates missingness in the primary endpoint (excluding death) by explicitly modeling the missing data mechanism, as described in Protocol Section 6.4.1.

In addition to the primary analysis using the main intent-to-treat (ITT) population, we will conduct sensitivity analyses using the classical ITT (cITT) and two modified ITT (mITT) analysis sets to assess the robustness of results.

Secondary endpoints

For quantitative secondary endpoints, including the key secondary endpoint of ventilator-free days (VFDs), we will apply the same analytic approach as described for the primary endpoint (RSFDs), including both unadjusted and adjusted methods using the semiparametric efficient and robust procedure proposed by Davidian et al. [7, 8]. In addition, analyses will be conducted on total RSFDs without the last-off approach, to assess consistency across definitions.

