In the GRAIL Phase 2 trial, VFDs difference was estimated to be 2.74 days. As shown in Table 6-2, to detect a similar difference (of 2.74 days) in RSFDs between the two arms with 85% statistical power, a sample size of 426 subjects ($213 \times 2 = 426$) total is required in this Phase 3 trial's primary analysis, and that is what we power for in this study. Findings from previous RCTs suggest that approximately 12% of subjects in this Phase 3 RCT will be CMV PCR positive at baseline when rapid lateral flow assay is used to assess serostatus. This 12% estimate is lower than the proportion reported in the GRAIL Phase 2 study due to the use of the rapid lateral flow assay, which we estimate will shorten the time to randomization from ICU admission by approximately 1 day and reduce the baseline PCR positivity rate. Furthermore, we anticipate that the percentage of subjects who are PCR positive at baseline will be lower among individuals on respiratory support (as defined in Section 4.1.1) compared with individuals on mechanical ventilation alone (as in the GRAIL Phase 2 trial) because we will be capturing some eligible participants earlier in the course of their respiratory failure when less time has elapsed to allow for CMV reactivation (both because we will allow enrollment of patients on NIV and HFNC oxygen and because time to obtain consent from participants able to consent for themselves may be shorter than consent through LARs. Since the population for primary analysis includes all patients without regard to PCR positivity at baseline, we inflate the sample size by a factor to

account for the power loss by including these cases in our primary analysis population. We also assume a dropout rate of 1% lost to follow-up for the primary endpoint, based on findings from other large ICU trials, and a dropout rate of 2% for early discontinuation following a negative CLIA CMV ELISA test among randomized participants who have received at least one dose of study drug. Accounting for both of these effects, the sample size for GRAIL Phase 3 trial was increased to 500 subjects in total.

6.1.2 Power Calculations for Secondary Endpoints.

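### SAP section 10 makes VFDs and ICU-free days missing for anyone who withdraws, even where day-28 chart data exist; the RSFD rule in section 8 is narrower, and the two should match (minor)

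*SAP*

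**What the plan says.** SAP section 10, item 1 (VFDs) and item 7 (ICU-free days), each carry the same bullet: "Participants who withdraw from the study will be considered as having missing data". Neither qualifies it by reason for withdrawal or by availability of data. Item 1 also scores deaths: "Participants who do not survive through Day 28 will be assigned 0 VFDs".

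SAP section 8 handles RSFDs differently. The value is missing for participants who withdrew consent or refused further participation "and for whom no further data were collected, or who withdrew due to study closure within the first 28 days".

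SAP 3.1 says that, for participants withdrawn after at least one dose, "clinical data available in the medical record (e.g., respiratory-support-free days) will continue to be collected per protocol", and it keeps them in the ITT set, which is the primary analysis population. Protocol 7.5 says the same, within what the signed consent allows. Among the reasons for withdrawal, SAP 3.1 lists "an initial positive CMV LFA test followed by a confirmatory negative CMV ELISA result". Protocol 6.1.1 plans for "a dropout rate of 2% for early discontinuation following a negative CLIA CMV ELISA test among randomized participants" who have had at least one dose.

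Section 10 items 2 (total RSFDs), 4 (ventilation duration in survivors) and 5 (respiratory-support duration in survivors) state no withdrawal rule.

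**The concern.** RSFDs and VFDs are built from the same daily chart record over the same 28 days. A participant withdrawn after dosing because the ELISA came back negative, or because the investigator ended participation, still has that record. Section 8 would count the RSFD. Section 10, as worded, would set the VFD and ICU-free-day values to missing.

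Two things are at stake. Data already collected would be left out of the ITT analysis of the key secondary endpoint, which would in effect move that analysis toward the first mITT set, defined separately to exclude withdrawn participants. And the primary and key secondary results would rest on different participants, which makes them harder to read side by side. On the same literal reading, item 4 ("Duration of mechanical ventilation among participants who survive through Day 28, the total number of days on invasive mechanical ventilation will be calculated") could count a withdrawn survivor whose VFD in item 1, derived from the same ventilator days, is missing.

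**Working it through.** **1. The plan's own sample size.** Inputs (SAP 2.5, protocol 6.1.1): difference 2.74 days, SD 9.4, two-sided 5%, power 85%. Both come from phase 2 VFD data (means 19.07 and 16.33), so they apply directly to VFDs.
- Normal approximation: n = 2 × (1.960 + 1.036)² × (9.4/2.74)² = 211.3, rounded up to 212 per arm.
- Two-sample t-test solution: 212.3, rounded up to 213 per arm, 426 in total. This reproduces the plan.
- Inflation: 426 / 0.97 / 0.88 = 499, close to 500. The 0.97 is the 1% lost to follow-up plus the 2% ELISA-negative. The 0.88 is an assumption, since the protocol gives 12% baseline PCR positivity but no explicit factor.

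**2. Participants on whom the two rules disagree.** Planned ELISA-negative withdrawals after dosing: 0.02 × 500 = 10 (binomial 95% range 4 to 17). Cross-check from assay performance in protocol 2.6 (97% sensitivity and specificity, 60% seroprevalence): PPV = 0.582 / (0.582 + 0.012) = 0.980, so 500 × 0.0202 = 10.1 false positives if all 500 entered on a positive lateral flow test.

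**3. Missing values under each rule, at N = 500.** This assumes that the ELISA-negative participants are not already among the missing RSFDs.

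| Source for missing RSFDs | RSFD missing | VFD missing, literal rule |
|---|---|---|
| Protocol 6.1.1, 1% lost to follow-up | 5 | 5 + 10 = 15 (3%) |
| SAP 3.2, about 2% | 10 | 10 + 10 = 20 (4%) |

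Both stay under the 5% level at which protocol 6.4.1.1 would model missing RSFDs.

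**4. Precision.** Standard error of the difference = SD × √(4/N).
- N = 495: 9.4 × √(4/495) = 0.845.
- N = 485: 9.4 × √(4/485) = 0.854.
- Ratio 1.010, a rise of about 1%. Power at 2.74 days goes from 90.0% to 89.4%.

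**5. Scale per participant for other withdrawals.** The documents give no count for withdrawals due to severe side effects, investigator decision or wrongful enrolment, so only a per-participant figure is possible. Take an arm of 250 and the phase 2 means:
- Removing one participant with VFD 0 raises the arm mean by 16.33/249 = 0.066 (placebo) or 19.07/249 = 0.077 day (ganciclovir).
- Removing one with VFD 27 lowers it by 10.67/249 = 0.043 or 7.93/249 = 0.032 day.

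**6. Who is unaffected.** For late starters found before five doses, protocol 7.5 stops data collection and removes them from the primary population. Those who ask for all their data to be deleted have none to use. Neither group changes under any wording.

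**The case against.** The best case for the plan is that the bullet is shorthand for section 8. SAP section 5 and protocol 6.2.2 say quantitative secondary endpoints are analysed as the primary endpoint is. SAP section 12, on changes from the protocol, declares no change in VFD data handling. Alternatively, the verb in section 10 could mean self-withdrawal only, since SAP 3.1 and protocol 7.5 mostly describe terminated participants in the passive. On either reading the count of 10 falls to zero.

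Much of this stands: the shorthand reading is plausible, and the 10 must be presented as a literal-reading figure. It does not remove the point. The SAP states neither reading, and a general sentence on method in section 5 does not clearly override a specific bullet in section 10. SAP 3.1 counts a negative ELISA as a withdrawal reason. Under the self-withdrawal reading, someone who refuses participation but whose chart data are still collected has an RSFD and no VFD.

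It is also fair that the cost is small: 3% missing equals the 1% plus 2% dropout already in the sample size, and the primary endpoint is untouched.

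Two stronger readings are tempting and should not be drawn. A reader might infer that a withdrawn participant who dies by day 28 could be scored either 0 or missing. Zero for death is part of the VFD definition in SAP 2.2 and protocol 5.2.1, with no exception, which favours 0; stating the order is only a tidy-up. A reader might also infer that withdrawal after day 28 erases a complete value. VFDs and ICU-free days cover only the first 28 days, so that reading is strained.

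**Conclusion.** The point holds as a minor inconsistency in wording. Followed literally, section 10 discards collected VFD and ICU-free-day data and analyses VFDs in different participants from RSFDs. The size is about 10 of 500, with a standard error about 1% larger. This rests on the literal reading, the planned 2% rate and the planned enrolment of 500. Enrolment closed early (SAP section 4), so the actual count may be lower; the documents do not give it.

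A reader might infer that the VFD comparison is biased. The documents do not show that. ELISA status is determined from the screening sample and should balance between arms. Withdrawals for safety or investigator reasons may depend on treatment, but neither their number nor their outcomes are given, so no direction can be claimed.

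**What to change.** Replace the withdrawal bullet in SAP section 10, items 1 and 7, with: *For participants who withdraw or are withdrawn, medical-record data through day 28 will be used where available, and death by day 28 is scored 0. The value is missing only when day-28 status could not be obtained (the section 8 rule, including study closure before day 28 with no further data).*

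Apply the same rule to items 2, 4 and 5. The death score applies to item 2 only, because items 4 and 5 are restricted to survivors. The last clause matters because section 8 can be parsed as making every study-closure withdrawal within 28 days missing, chart data or not. Section 8 should carry the same qualifier so that the endpoints agree.

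The cost is one sentence and no new data collection. The downside is that VFDs will include ELISA-negative participants who cannot benefit, as RSFDs already do. The first mITT set, if applied to VFDs as it is to RSFDs, would show the result without them.
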